### **Your blood pressure measurements:**

Attended Blood Pressure*	Unattended Blood Pressure*
Systolic Blood Pressure: _____ mmHg	Systolic Blood Pressure: _____ mmHg
Diastolic Blood Pressure: _____ mmHg	Diastolic Blood Pressure: _____ mmHg
Heart Rate: _____ beats per minute	Heart Rate: _____ beats per minute

\*Average of six blood pressure measurements.

**Based on 2017 guidelines from the American College of Cardiology and American Heart Association, categories of clinic blood pressure are defined as follows:**

Blood Pressure Category	Systolic Blood Pressure		Diastolic Blood Pressure
Normal	<120 mm Hg	and	<80 mm Hg
Elevated	120-129 mm Hg	and	<80 mm Hg
Hypertension			
Stage 1	130-139 mm Hg	or	80-89 mm Hg
Stage 2	≥140 mm Hg	or	≥90 mm Hg

This is based on average of the blood pressure readings taken during your first two clinic visits.

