Median (min – max)	118.2 (92.2 - 179.5)	117.5 (92.2 - 179.5)	118.7 (95.2 - 170.7)	118.3 (94.2 - 161.2)	117.8 (92.2 - 179.5)
Diastolic BP					
Mean (SD)	72.7 (7.8)	72.5 (7.9)	72.9 (7.8)	72.7 (7.5)	72.7 (8.1)
Median (min – max)	71.5 (53.5 - 97.7)	71.0 (53.5 - 97.7)	71.7 (54.8 - 96.3)	71.6 (53.5 - 95.5)	71.3 (59.2 - 97.7)
Unattended office blood pressure					
Systolic BP					
Mean (SD)	118.7 (11.8)	118.2 (11.8)	119.2 (11.8)	119.0 (11.6)	118.3 (12.1)
Median (min – max)	117.3 (90.5 - 179.8)	116.8 (90.5 - 179.8)	117.8 (95.2 - 179.0)	117.7 (91.7 - 158.5)	116.8 (90.5 - 179.8)
Diastolic BP					
Mean (SD)	72.2 (7.7)	71.8 (7.8)	72.5 (7.6)	72.1 (7.5)	72.2 (7.9)
Median (min – max)	71.0 (47.2 - 98.5)	70.8 (47.2 - 98.5)	71.4 (55.7 - 96.8)	71.3 (47.2 - 94.5)	70.8 (57.8 - 98.5)

Table 1 continued.

Ambulatory blood pressure monitoring					
Awake systolic BP					
Mean (SD)	118.7 (10.2)	118.4 (10.4)	119.1 (9.9)	119.2 (10.0)	118.3 (10.4)
Median (min – max)	117.8 (87.6 - 172.8)	117.3 (87.6 - 172.8)	118.3 (97.5 - 154.5)	118.3 (96.7 - 154.5)	117.5 (87.6 - 172.8)
Awake diastolic BP					
Mean (SD)	74.2 (7.0)	73.8 (7.0)	74.6 (7.0)	74.4 (6.8)	74.0 (7.2)
Median (min – max)	73.3 (52.9 - 98.9)	73.1 (52.9 - 94.0)	73.7 (60.3 - 98.9)	73.5 (60.3 - 91.3)	73.1 (52.9 - 98.9)
Asleep systolic BP					
Mean (SD)	104.1 (10.5)	104.0 (10.5)	104.1 (10.5)	104.7 (10.6)	103.4 (10.3)
Median (min – max)	103.2 (72.3 - 145.0)	103.0 (77.1 - 145.0)	103.3 (72.3 - 139.4)	103.6 (78.6 - 145.0)	102.8 (72.3 - 136.1)
Asleep diastolic BP					
Mean (SD)	60.3 (7.5)	60.3 (7.7)	60.3 (7.4)	60.4 (7.4)	60.1 (7.6)
Median (min – max)	59.7 (42.1 - 95.4)	59.6 (43.2 - 95.4)	60.2 (42.1 - 89.3)	59.7 (45.1 - 95.4)	59.9 (42.1 - 89.3)
Home blood pressure monitoring					
Asleep systolic BP					
Mean (SD)	106.3 (11.6)	106.5 (11.3)	106.2 (12.0)	105.7 (11.7)	106.9 (11.6)
Median (min – max)	106.0 (74.0 - 159.0)	107.0 (74.0 - 155.0)	105.0 (81.0 - 159.0)	106.0 (80.0 - 159.0)	107.0 (74.0 - 155.0)
Asleep diastolic BP					
Mean (SD)	62.3 (8.3)	62.5 (8.1)	62.1 (8.5)	61.8 (8.3)	62.9 (8.3)
Median (min – max)	62.0 (38.0 - 88.0)	62.0 (42.0 - 85.0)	62.0 (38.0 - 88.0)	61.0 (38.0 - 88.0)	62.0 (44.0 - 86.0)
Hypertension, %	40 (6.6)	25 (8.3)	15 (5.0)	17 (5.6)	23 (7.6)
High cholesterol, %	56 (9.3)	28 (9.3)	28 (9.3)	29 (9.6)	27 (9.0)
Diabetes, %	10 (1.7)	2 (0.7)	8 (2.6)	5 (1.7)	5 (1.7)
Asthma or hay fever, %	68 (11.3)	32 (10.6)	36 (11.9)	32 (10.6)	36 (12.0)

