**Table 2. Limitations of published studies comparing attended and unattended BP versus awake BP on ABPM**

1. The order of clinic BP measurement (attended and unattended clinic BP) was not randomized. In prior studies, unattended clinic BP was performed after attended clinic BP. Thus, order effects cannot be excluded.
2. Attended clinic BP was not measured in a standardized way (guideline recommendations). The difference in unattended and attended BP could be explained by poor measurement techniques when obtaining attended BP.
3. Attended clinic BP was measured by auscultation using a mercury sphygmomanometer. In the US, this method is no longer performed, and oscillometric devices have become a common method for BP measurement in practice.
4. Enrollment was restricted to patients with high clinic BP. Enrollment of patients with only high clinic BP makes it impossible to separate the effect of unattended clinic BP measurements from regression to the mean. Few data are available comparing unattended and attended clinic BP among adults with normal clinic BP or prehypertension.
5. Patients often were taking antihypertensive medication. The role of unattended clinic BP measurement for the initial diagnosis of hypertension (which is the focus on the proposed study) remains unclear.
6. Studies have focused on the diagnosis of white coat hypertension. Scarce data are available from studies evaluating the effect of measuring unattended BP on masked hypertension. An unintended consequence of unattended BP is that it may increase the prevalence of masked hypertension as individuals who would have previously been identified as having sustained hypertension (elevated clinic BP and awake BP on ABPM) will now have masked hypertension because clinic BP is no longer elevated.  However, if unattended clinic BP measurement provides an accurate estimate of awake BP on ABPM, then the prevalence of masked hypertension should decrease.

**B.6.2. New approach for assessing sleep BP.** Recently, home BP monitors (HBPM) have been adapted to measure asleep BP. As described below, there are compelling preliminary data supporting this approach.

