- Mean screening SBP of 110 to  $< 160$  mm Hg and mean screening DBP of 70 to  $< 100$  mm Hg based on the two most recent outpatient clinic visits, extracted from clinical records. As people with clinic SBP  $< 110$  mm Hg and DBP  $< 70$  mm Hg are very unlikely to have masked hypertension, we will not include these participants in our study. Also, people with clinic SBP  $\geq 160$  mm Hg or DBP  $\geq 100$  mm Hg are typically referred for additional BP management with a high percentage initiated on antihypertensive medication.

Exclusion criteria are:

- Lack of willingness to provide written informed consent.
- Use of antihypertensive or other medications that substantially affect BP (e.g., NSAIDS, steroids).
- History of CVD or major arrhythmias (e.g. atrial fibrillation, ventricular tachycardia).
- *Individuals who work second shift or overnight, as diurnal BP patterns may be different for this group, or with jobs that will not allow the ABPM device to measure BP every 30 minutes (e.g., truck drivers).*
- *History of sleep apnea by self-report, identified in their clinic records, and/or a score  $\geq 3$  on the STOP-BANG questionnaire. The sensitivity of a STOP-BANG score  $\geq 3$  for identifying sleep apnea is 90%.*
- *Orthostatic hypotension assessed during the screening visit (Section D.5). Mean awake BP on ABPM may be affected by hypotensive episodes during standing or walking.*
- Pregnancy (as no ABPM devices have been validated in pregnant women).

*Although there is no estimated glomerular filtration rate (eGFR) exclusion criteria, we anticipate the prevalence of an eGFR  $< 60 \text{ ml/min/1.73 m}^2$  will be low. Only 3% of US adults not taking antihypertensive medication in NHANES 2011-2014 had an eGFR  $< 60 \text{ ml/min/1.73 m}^2$ . We will adjust for eGFR in multivariable analyses.*

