**D.4.2. Recruitment by race-ethnicity.** Nighttime BP differs substantially by race/ethnicity. We will not exclude people on the basis of race/ethnicity. To provide statistical power to detect differences in the validity of study results by race-ethnicity, we will recruit at least 160 white, 160 African American and 160 Hispanic participants. In a preliminary query of the I2B2 database, there were over 50,000 whites, 40,000 African Americans and 3,000 Hispanics who met the eligibility criteria at UAB in 2016. At Columbia, over 550 African Americans and 900 Hispanics have been enrolled in our recent studies of ABPM and HBPM.

**D.4.3. Recruitment by BP levels.** To ensure a broad range of clinic BP values for the current study, we will recruit 50% of our sample to have SBP  $\geq 140 \text{ mm Hg}$  or DBP  $\geq 90 \text{ mm Hg}$  based on the average of the most recent two clinic visits in their medical record.

**D.5. Screening visit.** Participants will have BP measured three times in each arm (as recommended by AHA guidelines) to determine which arm (one with higher mean BP) to use for assessing clinic BP and to confirm participants do not have orthostatic hypotension. The arm with the higher BP will be used for all BP measurements obtained during the study. For assessment of orthostatic hypotension, additional readings will be obtained after the participant has been supine for at least 5 minutes and after both 1 and 3 minutes of standing. Orthostatic hypotension will be defined as a maximum decline in SBP from supine to standing  $\geq 20 \text{ mmHg}$ . We will use the STOP-BANG Questionnaire to assess the probability of having sleep apnea. Those with a STOP-BANG score  $\geq 3$  will be considered to have a high probability of sleep apnea and excluded from enrollment.

**D.6. Study visits.** After obtaining consent, the protocol involves eight domains of data collection (Table 4). Data will be collected over one to two weeks during four study visits (Figure 3). The protocol is similar in complexity to ones we have implemented in the IDH and MHT studies and the AHA-SFRN.

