#### **D.10.2. Data transfer.**

**D.10.2.1. ABPM, sleep HBPM, actigraphy, and Device Logs.** Upon return of the ABPM, HBPM, actigraph, and Device Logs, data will be downloaded to a computer and then backed up to a secure network server. Data will be transferred daily to the PEER Unit at UAB using DatAnywhere, a HIPAA compliant file transfer protocol that we used in our AHA-SFRN study. Monthly reports that track data quality will be generated. If data issues are identified (e.g., frequent ABPM or HBPM reading errors), staff will be re-trained.

**D.10.2.2. Echocardiographic measures.** The echocardiographic studies (with unique study identifiers; i.e. de-identified) will be saved to DVD/CD, and backed up to secure research servers at each site. The studies at UAB will be sent to the Cardiovascular Physiology Research Laboratory at Columbia for analysis.

**D.10.3. Data management and cleaning.** All data cleaning will be managed by a statistician at the UAB PEER Unit supervised by [name]. A uniform data editing algorithm, established by Drs. [name] and [name] and used in prior studies, will be implemented to confirm acceptability of the ABPM data and exclude extreme outliers. Minimal editing is the general rule; less than 0.1% of readings are typically excluded. The awake and sleep periods on ABPM will be defined by the actigraphy recording, complimented by self-report

awake and sleep periods from the Device Log. For sleep BP on HBPM, we will confirm that participants were asleep when the the BP readings were obtained using actigraphy data and the HBPM Device Log.

**D.10.4. Minimum number of BP readings required on ABPM and HBPM.** No consensus exists on the number of readings required to consider an ABPM recording complete. Consistent with our prior studies, we will require 14+ awake BP readings, and 5+ sleep BP readings, and  $\geq 80\%$  of the planned 48 readings (39+ total valid readings). We will require three SBP and DBP readings for a sleep HBPM recording to be complete. We will continue recruitment until 600 participants have complete ABPM and sleep HBPM readings.

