**Protection against risks:** The physical risks of the studies are minimal, as no invasive procedures are proposed. Some discomfort may occur due to the use of the arm cuff for measuring blood pressure, and no/minimal discomfort is expected with using the actigraph device. The discomfort from the blood pressure cuffs, if it occurs, is temporary and should disappear when the cuffs are removed. Any discomfort, if it occurs, is minimal and temporary. The risks of having blood drawn include soreness and bruising at the puncture site, and sometimes there may be discomfort during the procedure. Occasionally participants feel lightheaded or faint. This may occur with the assessment of orthostatic hypotension as well. The assessment of orthostatic hypotension and the blood draw will occur in the presence of trained technicians with training handling safety issues for participants. A minimal risk to participants arises from the release of study data. To minimize this risk, staff conducting study visits will be trained in the protection of human subjects. In addition, all study information and the study computer will be kept in a locked room in at the participating field center and University of Alabama at Birmingham. The computer databases will be encrypted and protected by a

password available only to study investigators and other personnel who need access. The link between patient identity and a unique study identification number will be destroyed after the study is completed. Published reports will contain only aggregate and statistical results, and no individual results or patient identifiers will be disclosed. These safeguards make the possibility of a breach of confidentiality or invasion of privacy remote.

**Very high or low clinic BP.** Individuals with mean screening SBP of 110 to < 160 mm Hg and mean screening DBP of 70 to <100 mm Hg (based on the two most recent outpatient clinic visits, extracted from clinical records) will be included. Therefore, we are not including individuals with severely high or low clinic BP. Among enrolled participants, if clinic BP at any of the study visits  $\geq 160/100$  mmHg or <110/70 mmHg they will be referred to their health care provider for evaluation and excluded from the study for safety reasons.

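### Section E.1.2 automatically excludes enrolled participants on their study-visit clinic BP, the measurement under evaluation; drop the low limit, make the high limit a clinical decision, and report who met it

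*Combined protocol and SAP*

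**What the plan says.** E.1.2, in its paragraph on very high or low clinic BP, applies to people already enrolled. If clinic BP at a study visit reaches 160/100 or falls below 110/70 mm Hg, "they will be referred to their health care provider for evaluation and excluded from the study for safety reasons". The wording is mandatory. It does not say whether the attended or the unattended value counts, whether one reading or a mean counts, or how systolic and diastolic combine.

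The same limits appear at entry. D.4.1 explains the low one: people below both values "are very unlikely to have masked hypertension, we will not include these participants in our study". It explains the high one by referral and the likely start of treatment. The manual's Blood Pressure Screening Procedures apply the limits before Visit 1, making a person ineligible if either component is high or if both are low.

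Three other parts bear on the point:
- D.4.3 recruits half the sample at 140/90 or above. Its stated aim is "To ensure a broad range of clinic BP values for the current study".
- D.10.4 says "We will continue recruitment until 600 participants have complete ABPM and sleep HBPM readings".
- The SAP restricts each comparative BP and organ-damage analysis to people with complete data and never mentions the E.1.2 rule.

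The manual has its own Blood Pressure Safety Protocol, but its content is a figure that is not shown. The visit forms contain no exclusion step.

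**The concern.** Visit 1 and 2 clinic BP is the quantity compared with awake BP in Aim 1 and related to LVMI and ACR in Aim 3. Removing people because of its value truncates that variable. Those who remain have clinic values that are too high relative to their awake values when the low end is cut, and too low when the high end is cut. The clinic range behind the Aim 3 associations also narrows.

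The loss would not show in the analysis set. At Visit 2, clinic BP is taken before the ABPM device is fitted (D.6.2), so a person removed for BP would simply lack awake data and fall out under the completeness filter. Recruiting on to 600 complete would restore the number but not undo the selection. The sample size allows 5% loss and nothing for this rule.

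**Working it through.** **The plan's own enrolment figure.** D.12.1 gives 630 enrolled, 5% lost, 600 complete. 630 × 0.95 = 598.5 and 600 / 0.95 = 632, so the figure reproduces without any BP exclusion.

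**Inputs for a sample like the one reported.** Means and SDs come from SAP Table 2 (N = 569). Systolic: attended 119.4 (12.1), unattended 118.7 (11.9), awake 118.7 (10.2). Diastolic: 72.7 (7.8), 72.2 (7.7), 74.2 (7.0). Correlations come from the Table 2 intervals, with SD of difference = (half-width / 1.96) × √569 and r = (s₁² + s₂² − SD²) / (2s₁s₂).
- Attended-awake systolic: 0.665 / 1.96 × 23.85 = 8.09; r = (146.41 + 104.04 − 65.50) / 246.84 = 0.75.
- Likewise unattended-awake 0.76 and attended-unattended 0.95.
- Diastolic: 0.70, 0.69 and 0.94.

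The systolic-diastolic correlation is not given; 0.5 to 0.8 is assumed.

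**Rule applied.** On either method's two-visit mean: systolic ≥160 or diastolic ≥100, or both systolic <110 and diastolic <70.

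**Results by simulation:**

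| Model | Removed | Shift in attended minus awake systolic |
|---|---|---|
| Normal | 18.0-23.0% | +1.17 to +1.58 |
| Screening limits built in | 17.0-23.3% | +1.00 to +1.53 |
| Right-skewed | 19.7-24.6% | +1.10 to +1.47 |

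- Attended minus awake moves from +0.7 to between +1.7 and +2.3 mm Hg.
- The high limit alone removes 0.1-0.5%.
- Attended minus unattended stays at 0.68-0.74.
- Attended systolic SD falls from 12.1 to 9.3-10.7, and its correlation with LVMI from 0.30 to 0.23-0.27.
- Hypertension, white coat and masked prevalences rise by a factor of 1.2-1.3. This is mostly a smaller denominator: 1 / (1 − 0.18) = 1.22 and 1 / (1 − 0.23) = 1.30.

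**Any single visit as the trigger** (between-visit r 0.7-0.85 assumed): 25-36% removed, shift +1.4 to +2.2 mm Hg.

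**Planned population, all inputs assumed.** Chart mean 122-130/78, SD 15/10, cut to the entry range, half at 140/90 or above, giving study-visit means of 125-136/78-84. On two-visit means, 3.6-11.4% are removed and the shift is −0.18 to +0.81 mm Hg.

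**Enrolment for 600 complete**, 600 / 0.95 / (1 − removed): about 760-840 for a reported-type sample and 660-710 for a planned-type one, on two-visit means.

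**Was the rule enforced?** The results packet describes each clinic value as an "Average of six blood pressure measurements", and Table 1 fits that: 967 / 6 = 161.2 and 553 / 6 = 92.2. Table 1 gives maximum mean attended systolic values of 179.5 (attended first, HBPM first), 170.7 (unattended first) and 161.2 (ABPM first). Since 161.2 is the ABPM-first maximum, the other two are HBPM-first, and those two had opposite clinic orders. They are three different people, 3 / 603 = 0.5%. A mean ≥160 requires at least one visit ≥160. All three were kept, and 179.5 is still in Table 2.

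**The case against.** The strongest reply is that E.1.2 is grant text which the manual replaces on several points: the clinic device, the rest period, the arm and the sleep-apnoea cut-off. The manual's safety protocol cannot be read, so the governing rule is unknown. Results are already tabulated, so deleting the rule changes no existing data. This stands, and it makes reconciliation and a count the main practical gain. It does not make the written rule sound.

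Four stronger readings are tempting and not supported.

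- **The reported results are biased.** Table 1 shows people past the high limit retained. That proof needs systolic or diastolic to suffice, as in the manual and the D.4.1 rationale; if both were required it fails, because mean diastolic peaks at 97.7 attended and 98.5 unattended. For the low limit nothing is provable. The lowest attended systolic means (92.2, 94.2, 95.2) probably came with diastolic below 70, but joint values are not shown.
- **The planned trial would lose a fifth.** That figure applies the grant's rule to the lower-BP sample actually recruited. In the population the grant intended, the estimate is 4-11%.
- **The plan condemns its own rule.** The grant's Table 2 says that restricted enrolment "makes it impossible to separate the effect of unattended clinic BP measurements from regression to the mean", but it is criticising studies that enrolled only people with high clinic BP. E.1.2 sets a two-sided band matching entry. Randomised order within each person is also untouched.
- **Removed people would go unreported.** D.15 already promises a flow diagram of how the final sample was derived. It does not promise a count for this criterion.

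The high limit does have a clinical reason. Referral plus clinical judgement meets it.

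**Conclusion.** The concern holds as a fault in the written plan. E.1.2 orders automatic post-randomisation selection on the measurement under test, and its low limit has no stated safety basis beyond the label.

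The cost depends on the population: 17-25% removed and +1.0 to +1.6 mm Hg on clinic minus awake systolic BP in a sample like the one reported; 4-11% and a small shift of unfixed sign in the planned one. The effect falls on agreement with awake BP, on prevalence and on the Aim 3 range. The attended-unattended difference is essentially unaffected.

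These sizes rest on the either-high, both-low reading, two-visit means and an assumed systolic-diastolic correlation. E.1.2 as worded, with any visit as trigger, would remove more. If one low component were enough, as the joint inclusion wording in D.4.1 could suggest, about half would go (48-51%). At least three people past the high limit were kept on the reading used here, so the rule was not uniformly enforced. Confidence is medium, because the documents do not show which rule governed.

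**What to change.** 1. Delete the automatic exclusion for the low limit.
2. For the high limit, keep referral. Allow withdrawal from further procedures on clinical judgement, and retain all data already collected.
3. Make E.1.2, the manual's Blood Pressure Safety Protocol and the SAP state one rule.
4. Add a SAP sentence that all recorded data are analysed whatever the study-visit BP.
5. In the flow diagram promised in D.15, report by limit how many met the criterion and how many, if any, were removed. Anyone removed before ABPM fitting has no awake BP and can only be counted.

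Cost: a wording change that may need IRB notice or review because it removes a stated safety exclusion, one SAP sentence, and a count from data already held.

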#### **E.1.3. Potential Benefits of the Proposed Research to the Subjects and Others**

There is a limited direct benefit to the study participants. Participants will receive a report containing information from their clinic blood pressure measurements, 24-hour ambulatory blood pressure monitoring and sleep blood pressure. This report will contain mean blood pressure from ambulatory monitoring, information on the presence of masked and white coat hypertension as well as information on the level of their blood pressure variability and diurnal blood pressure patterns. Drs. [name], [name], [name], and [name] have over 50 years of cumulative experience preparing reports with results and interpretation for study participants. Although ambulatory blood pressure monitoring is not commonly used in clinical practice, some participants (and their physicians) may find the results of the ambulatory blood pressure monitoring helpful. Reports will be provided to participants within one month of completion of their study visit. As the risks to subjects are minimal, and important prognostic medical information not typically accessible to subjects will be made available, the benefits are considered to outweigh the risks.

